**Cohort entry (index date) for exposed:**

- 1) Date of initiation of the second administration/filled prescription of the conventional systemic therapy for AD,
- 2) Last inclusion date is December 31st, 2021, to allow for a minimum of one year of follow-up.

### 8.2.1. Inclusion Criteria

Patients must meet all of the following inclusion criteria to be eligible for inclusion in the study:

1. Age ≥18 years at prescription/administration of conventional systemic therapy
2. An ICD-10 diagnostic code for AD provided by a dermatologist (Table I)
3. Have filled/administered the same conventional therapy twice (Table II)

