**Time period**

The study period runs from January 1st, 1995, through December 31st, 2022. In the main analyses, patients are included if they have been diagnosed with AD by a dermatologist in a hospital setting and received the same conventional systemic therapy twice (Table II).

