### 8.2.2. Exclusion Criteria

Patients meeting any of the following criteria will not be included in the study:

1. Current or previous cancer prior to inclusion (except NMSC) (Table III)
2. History of biological therapy prior to inclusion (Table II)
3. History of JAK inhibitor prior to inclusion (Table II)
4. History of prespecified diseases that could be treated with the conventional drugs of interest i.e., RA, IBD, PsA, and PsO (Table I)

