### Follow-up and exposure and censoring

Patients are followed from the index date until the earliest occurrence of one of the following: the event of interest, the study closing date (30 December 2022), initiation of a

biological therapy or JAK inhibitor, death, the development of a condition that would qualify for one of the treatments of interest (Table 1), or migration.

When using treatment series, exposure time is calculated and cumulated based on the specific therapy received. Except for the event of interest, any of the previously mentioned cases will result in censoring.

Additional analyses will be conducted on an intention-to-treat basis.

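### The dermatologist AD code need not precede the index date, so patients first coded after their second fill can be enrolled with guaranteed survival up to that code

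*Protocol*

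**What the plan says.** Eligibility and entry are set in Protocol section 8.2.

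- Inclusion criterion 2 (8.2.1) asks for "An ICD-10 diagnostic code for AD provided by a dermatologist (Table I"). It gives no date or order.
- The time-period paragraph says that "patients are included if they have been diagnosed with AD by a dermatologist in a hospital setting and received the same conventional systemic therapy twice". The two conditions are joined without a sequence, over a study period running from 1 January 1995 "through December 31 st , 2022".
- The index date for the exposed is the "Date of initiation of the second administration/filled prescription of the conventional systemic therapy for AD".
- Section 8.7, on follow-up and censoring, says "Patients are followed from the index date until the earliest occurrence of one of the following". The AD code date plays no part.

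Neighbouring criteria do carry a time anchor. Inclusion criterion 1 reads "Age ≥18 years at prescription/administration of conventional systemic therapy". Exclusion criteria 1 to 3 (8.2.2) are tied to inclusion, for example "Current or previous cancer prior to inclusion (except NMSC) (Table III") and "History of biological therapy prior to inclusion (Table II").

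**The concern.** If the AD code may come after the index date, eligibility is decided with information from after follow-up has started. A patient who died between the second fill and a later AD code never enters the cohort. One who survived to be coded contributes the whole interval as person-time in which death was impossible.

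Three outcomes are directly exposed: all-cause mortality (secondary endpoint), CV death (a MACE component in Table III) and infections resulting in death (part of the serious-infection definition in 8.7). The error lowers the rate in the treated group, the unhelpful direction for a safety study. The general-population comparator needs no later AD code, so the tertiary comparison with it would be shifted as well.

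There is also a population problem. Every objective concerns a dermatologist-verified AD population, and section 8.2 says the criteria are meant to secure an accurate diagnosis and treatment directed at AD. Time on drug before any verifying code does not meet that description.

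**Working it through.** **Is there an ordering rule anywhere?** No passage on eligibility, index date or follow-up requires the AD code on or before index. The nearest wording is in the index-date rule, which describes the therapy as being for AD. That cannot be applied in the data: Table II identifies exposure only by ATC and SKS codes (for prednisolone, the whole H02AB group). Section 8.9 accepts that a study drug may have been prescribed for another diagnosis.

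**Worked case.** Take two qualifying fills in 1998, a first dermatologist L20.x code in 2012, and none of the exclusions. The patient meets every criterion as written and is followed from 1998. The immortal interval is 2012 − 1998 = 14 years.

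**Could late coding arise?** Section 8.4 says the prescription register covers community-pharmacy fills from 1995, while AD must be coded in hospital and outpatient visits are recorded only from 1995. Late first codes are therefore plausible, but the protocol does not count them.

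**Size, on assumed inputs.** No figure in the protocol depends on this point, so there is none to reproduce. Let q be the share of patients coded after index, L the mean lag in years and F the mean follow-up in years. None of the three is given.

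Immortal share of person-time: s = q × L / F. Observed rate / true rate ≈ 1 − s.

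A simulation checked this, with a constant true death rate of 100 per 10,000 person-years, 10 years of intention-to-treat follow-up and an exponential lag. Late-coded patients were kept only if they survived to a code within the 10 years.

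| q | L (years) | s = qL/10 | Simulated rate, follow-up from index | Simulated rate, entry at later of index and code |
|---|---|---|---|---|
| 20% | 1 | 2% | 97.9 | 99.9 |
| 20% | 3 | 6% | 94.9 | 100.0 |
| 20% | 5 | 10% | 94.2 | 100.3 |
| 30% | 1 | 3% | 96.6 | 99.7 |
| 30% | 3 | 9% | 92.2 | 99.9 |
| 30% | 5 | 15% | 90.5 | 99.8 |

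The simulated shortfall runs from 100 − 97.9 = 2.1% to 100 − 90.5 = 9.5%. At long lags the simple formula gives more, because it ignores lags beyond 10 years dropping out. For L = 5, a fraction e^(−2) = 0.135 of lags exceed 10 years, and the mean of the rest is 5 − 10 × 0.135/0.865 ≈ 3.4 years. The late share among those kept is 0.30 × 0.865/(0.70 + 0.30 × 0.865) ≈ 0.27. Hence s ≈ 0.27 × 3.4/10 ≈ 9%, in line with the simulation.

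Over a wider assumed range (q 5–30%, L 1–5 years, F 5–10 years), the formula gives 0.05 × 1/10 = 0.5% to 0.30 × 5/5 = 30%. The input range determines the answer.

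**Treatment-series analysis.** Only on-drug time counts here, so fewer person-years are touched in absolute terms, but a series that ends before the AD code is wholly immortal for death. The affected share would reach q itself only if every late-coded patient's series ended before the code and were as long as other patients' series. That is a ceiling, not an estimate.

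**The case against.** The strongest reply is that the protocol evidently intends diagnosis first. The time-period paragraph uses a perfect tense for the diagnosis, the index therapy is described as being for AD, and the rationale in 8.2 speaks of treatment directed at AD. The missing anchor is weak evidence of anything else: exclusion criterion 4 has no explicit anchor either, yet must mean history before index, because 8.7 censors patients who develop those diseases later. This stands as to intent. It does not supply a rule a programmer can apply, and entry and start of follow-up are fixed in this protocol rather than left to a later document.

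Some stronger readings are tempting but unsupported:

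- **That such patients are in the cohort in known numbers.** The text shows only that they can be enrolled.
- **That all primary rates are biased by immortal time.** The guarantee concerns survival. Non-fatal infarction, stroke, malignancy, zoster and thromboembolism can occur before the code and still be counted.
- **That affected patients cannot emigrate.** Someone may leave, return and be coded later, and 8.7 censors at migration.
- **That a childhood AD code followed by adult treatment is the same defect.** There the diagnosis precedes index, so no time is immortal. The question is treatment indication, which 8.9 already acknowledges. An adult-age code or a recency window would be a preference, not a correction.

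**Conclusion.** The point holds as a gap in the cohort definition. As written, the AD code may fall after the index date. Time from index to that code is then immortal for death and lies outside the verified population. The direction is certain for all-cause mortality, CV death within MACE and fatal infections: downward. For non-fatal outcomes the effect is indirect, mainly the counting of time and events under an unverified diagnosis.

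The size cannot be derived from the documents. The illustrative 2–10% understatement of the intention-to-treat death rate assumes 20–30% of patients coded late, a mean lag of 1–5 years, 10 years of follow-up and a constant hazard. A smaller share or a shorter lag would make it negligible. The rule should be settled before the cohort is built, because every mortality-related rate and comparison inherits it.

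**What to change.** Make one of two changes in 8.2 and carry it into 8.7:

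1. Amend inclusion criterion 2 to require at least one dermatologist-assigned L20.x hospital contact on or before the index date.
2. Alternatively, define cohort entry as the later of the first such contact and the second qualifying fill or administration, provided a treatment series is ongoing on that date. Count person-time and events only from then, and assess age and the exclusion criteria at that date.

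Apply the same rule to the untreated AD comparator, with the AD code on or before its assigned index date. If only the exposed cohort is corrected, the tertiary comparison between the two AD groups becomes asymmetric.

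The drafting cost is a few sentences, using diagnosis dates already needed from the patient registry. The data cost is some early person-time and some patients. It falls mostly on the first study years, because outpatient codes begin in 1995, so the 1995–2001 period in the calendar-time sensitivity analysis would be thinned most. Under the second option, late-coded patients enter part-way through a treatment series, which the report should state.

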**Inclusion criteria rationale:**

The objective is to increase the probability that the included patients have an accurate diagnosis (criteria 2) and are actively filling their prescriptions (criteria 3); this strategy may create a more selective cohort but seeks to ensure superior data quality.

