### Treatment series

Treatment series are defined as periods of time in which a patient is considered on active treatment. The allowable gap between administrations of the same drug is 150 days to aggregate the treatment series. If the gap exceeds 150 days, patients are considered to have initiated a new treatment series. The allowable gap is based on the common gap of 90 days between each filled prescription, with an additional extension of 60 days to mirror the design of ORALSURV, which allowed for up to 2 months of discontinuation for safety issues.

The duration of active therapy following the last filled prescription or administration is set at 120 days, reflecting the standard 90-day prescription interval plus an additional 30 days, as outlined by Fleischmann et al. . Each treatment series is considered separately, as concomitant therapies were allowed in the ORALSURV study design.

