**Patient characteristics:**

Descriptive statistics will be presented to describe patient characteristics performed for all groups:

- a) dermatologist-verified adult patient population with atopic dermatitis (AD) receiving conventional systemic treatments as per inclusion/exclusion criteria,
- b) cohort-matched general Danish population
- c) cohort-matched patients with AD not receiving systemic treatment (see section above for matching criteria).

Categorical covariates will be described by frequency distribution while continuous covariates expressed in terms of their mean and standard deviation or median and interquartile range (IQR) as appropriate. The descriptive statistics will be captured in a statistical report with aggregated data in tables.

Between group comparisons for baseline characteristics:

Pearson's chi-square test will be used for dichotomous categorical variables, t-test will be used for continuous variables, and the Mann-Whitney U test for non-parametric variables. The statistical analysis will be captured in a statistical report with aggregated data in tables.

Primary endpoint statistical analysis:

Incidence rates of major adverse cardiovascular events (MACE) and malignancy (excluding non-melanoma skin cancer (NMSC)) will be presented per 10,000 person-years at risk with 95% confidence intervals. The incidence rates will be reported for each group separately: a) a dermatologist-verified adult patient population with atopic dermatitis (AD) receiving conventional systemic treatments as per inclusion/exclusion criteria, b) cohort-matched general Danish population and c) cohort-matched patients with AD not receiving systemic treatment (see section above for matching criteria). For group a, the incident rates will be presented per individual conventional systemic treatment (see table II).

In cases where patients received two systemic treatments or more during the data collection period, each treatment series will be analyzed independently. The statistical analysis will be captured in a statistical report with aggregated data in tables.

In the primary analyses, overlapping events will be attributed to the drug to which the patient has been exposed for the longest duration.

Secondary endpoint statistical analysis:

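### The two-fill rule and second-fill index date govern patient entry, but rates are reported per drug, so as written a later drug can count from its first fill, or on a single fill

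*Protocol*

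**What the plan says.** **Entry.** Section 8.2.1 sets eligibility for the patient: "Patients must meet all of the following inclusion criteria to be eligible for inclusion in the study". The third criterion is "Have filled/administered the same conventional therapy twice (Table II". Its rationale in section 8.2 is that those included "are actively filling their prescriptions (criteria 3". Cohort entry for the exposed, also in section 8.2, is "Date of initiation of the second administration/filled prescription of the conventional systemic therapy for AD".

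**Follow-up and exposure.** Under the follow-up heading of section 8.7, "Patients are followed from the index date until the earliest occurrence of one of the following", and with treatment series "exposure time is calculated and cumulated based on the specific therapy received".

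**Series.** Section 8.7 (Treatment series) defines a series by two day rules. A gap of more than 150 days between fills of the same drug opens a new series, and "The duration of active therapy following the last filled prescription or administration is set at 120 days". It sets no minimum number of fills and no start at the second fill.

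**Reporting.** Primary and secondary rates in the treated group are given separately for each conventional drug in Table II. For patients with two or more drugs, "each treatment series will be analyzed independently". No sentence applies the two-fill rule, or a new index date, to a second drug or a restarted series.

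**The concern.** The rule that defines a confirmed user is attached to the patient, while the primary output is attached to the drug. Suppose a patient enters on methotrexate and later fills prednisolone once. On the literal text this patient adds a 120-day prednisolone series. A patient whose only fill was that same prednisolone course is not eligible. If the later drug is filled repeatedly, the interval between its first and second fill is counted. For the drug that brought the patient in, that interval lies before the index date and is dropped.

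Each drug's rate would then mix two exposure definitions, in proportions that depend on how often the drug is used first and how often after another. Part of any difference between drugs could reflect order of use. The Cox comparisons with the two matched cohorts are also made per drug and would inherit the mix. Prednisolone is the most exposed: Table II codes it broadly (H02AB*), and section 8.9 concedes that it may have been prescribed for something other than atopic dermatitis. For later drugs, nothing enforces the stated purpose of criterion 3.

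**Working it through.** **Inputs from section 8.7 (Treatment series).** Common interval between fills: 90 days. Allowable gap: 90 + 60 = 150 days. Tail after the last fill: 90 + 30 = 120 days. Both sums reproduce the protocol's figures. The protocol states no figure for the effect examined here.

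**Not given, so assumed.** Number of fills (2, 4 or 8); interval g (30 to 150 days, so that fills stay in one series); ratio k of the hazard in the first 90 days to the hazard afterwards (0.5 to 3); share s of later-drug series that are single fills (10% to 50%).

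**Step 1: person-time on the literal text.** For n fills at interval g, the full series lasts T = (n − 1)g + 120 days. The entry drug's first qualifying series counts T − g. A drug started after entry counts T. The extra share is g/T. With g = 90:

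| Fills | Entry drug, days | Later drug, days | Extra window as share of later drug's time |
|---|---|---|---|
| 1 | 0 (does not qualify) | 120 | all of it |
| 2 | 120 | 210 | 90/210 = 43% |
| 4 | 300 | 390 | 90/390 = 23% |
| 8 | 660 | 750 | 90/750 = 12% |

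For two fills with g from 30 to 150 days, the later drug counts 150 to 270 days against 120, and the share runs from 30/150 = 20% to 150/270 = 56%.

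**Step 2: effect on the rate.** Give both drugs the same true hazard, k times its later level during the first 90 days. The rate ratio, later-drug counting to entry-drug counting, is (90k + T − 90)/T:

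| k | 2 fills | 4 fills | 8 fills |
|---|---|---|---|
| 0.5 | 165/210 = 0.79 | 345/390 = 0.88 | 705/750 = 0.94 |
| 1 | 1.00 | 1.00 | 1.00 |
| 2 | 300/210 = 1.43 | 480/390 = 1.23 | 840/750 = 1.12 |
| 3 | 390/210 = 1.86 | 570/390 = 1.46 | 930/750 = 1.24 |

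**Step 3: adding single-fill series.** Let a share s of later-drug series be single fills (120 days) and the rest four fills (390 days), with the same hazard profile. The ratio is [s(90k + 30) + (1 − s)(90k + 300)] / [120s + 390(1 − s)]. At k = 2, s = 0.1 gives 453/363 = 1.25 and s = 0.5 gives 345/255 = 1.35. At k = 1 it is 1.00 for any s. If single-fill users have a different underlying risk, the ratio moves even at k = 1, by an amount the protocol gives no means to estimate.

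**Step 4: after the fix.** With a second-fill start for every drug, two fills 90 days apart count 120 days for both and a single fill counts 0 for both. The ratio due to counting alone is 1.00 for any k under this hazard profile.

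**The case against.** **A per-drug rule may be intended.** Section 8.7 considers each series separately, compares each drug with its matched cohorts, and lists the index date, glossed as the prescription date, among possible matching variables. All of this is compatible with an entry date for each drug. A reader might infer that the protocol expressly fixes one index date per patient, citing the sentence in section 8.7 (Events) about the treatment initiated at the index date. That goes too far: the sentence concerns only the intention-to-treat analysis and would also fit a drug-specific index date. What stands is that the per-patient reading is the natural one but is never explicit. No sentence states the per-drug rule either.

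**The contrast is not simply entry drug against later drug.** A reader might infer that the entry drug never contributes first-fill or single-fill time. On the same literal reading it does: a restart after more than 150 days opens a new series that counts from its own first fill. The contrast is exact only for the entry drug's first qualifying series.

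**The 43% is not a bias.** It is a share of person-time in the shortest qualifying course. A constant hazard gives no bias from the start date alone.

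**Other analyses help.** The one-use sensitivity analysis shows sensitivity to the two-fill restriction, and the intention-to-treat analysis attributes events to the index treatment. The first changes only the inclusion criterion and does not align drugs within the main analysis. The second is largely unaffected by the problem but is additional.

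**This is detail for the analysis plan.** How to program series usually is. But this protocol itself fixes eligibility and the index date, and does so at a level that does not match its primary output.

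**Conclusion.** The point holds as a defect in the written rule. Executed literally, the main analysis gives per-drug rates on unequal exposure definitions.

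If early risk is twice later risk, counting alone would raise a later drug's rate by 43%, 23% or 12% for two, four or eight fills at 90-day intervals. If early risk is half, it would lower the rate by 21%, 12% or 6%. These are illustrations. The true early-to-later ratio, the distribution of fills and the share of single fills are not in the protocol, so the actual size cannot be known. Direction is also open where drugs overlap: the primary rule assigns the event to the drug used longest, while exposure is cumulated by the therapy received. A brief later course could therefore add time to one drug while its event goes to another.

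Distortion requires early risk to differ from later risk, or single-fill users to differ from continuing users. That is most plausible for serious infection and herpes zoster, which are secondary endpoints, and for prednisolone. A reader might infer that the primary MACE and malignancy rates are materially wrong; nothing in the protocol supports that.

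**What to change.** In sections 8.2 and 8.7:

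- State that in the main treatment-series analysis a patient contributes person-time and events to a drug only from the second fill of that same drug. If two uses are required, time should start at the second; starting at the first would add immortal time.
- Check the prior-cancer exclusion at that drug-specific date. For outcomes other than malignancy, a cancer arising after cohort entry does not end follow-up. The other exclusions need no new check, because the censoring rules already cover biologics, JAK inhibitors and the Table I conditions.
- State how a restarted series of an already qualified drug is counted, and apply the same rule to every drug.
- In the one-use sensitivity analysis, start every drug at its first fill.

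The cost is a few sentences, a programming change and a small loss of person-time for drugs used after the entry drug. The discarded time remains available in the one-use sensitivity analysis.

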### 8.2.2. Exclusion Criteria

Patients meeting any of the following criteria will not be included in the study:

1. Current or previous cancer prior to inclusion (except NMSC) (Table III)
2. History of biological therapy prior to inclusion (Table II)
3. History of JAK inhibitor prior to inclusion (Table II)
4. History of prespecified diseases that could be treated with the conventional drugs of interest i.e., RA, IBD, PsA, and PsO (Table I)

